7.2 Day 1 (FIRST DOSE AND POST-DOSE)

NOTE: Day 1 is deemed to be the first 24 hours after enrollment into the study, with time 0 (time of first dose) occurring as quickly as possible after the subject's eligibility has been confirmed.

• Administer first dose (1800 mg) at time 0.

Following First Dose:

- For subjects randomized to favipiravir, collect blood sample for PK within 45 to 75 minutes post-dose
- Measure and record vital signs (BP, HR, Temp, Resp).
- Collect and record SpO2 by Finger Sensor
- Administer second dose (1800 mg) at time 0 + 12 hours.
- Perform limited PE to focus on heart and lungs (may be done by the Principal Investigator or their designee).
 - **NOTE:** to be done every day while the subject is in the hospital and on return study visits after discharge
- Collect and record adverse events (see Section 8.4 for detailed instructions)

7.3 Days 2 and 14

- Measure and record vital signs (BP, HR, Temp, Resp).
- Perform a limited PE to focus on heart and lungs.
- Review and record concomitant medications (Note: if there have been changes in concomitant medications during the study, determine whether the change is due to an AE).
- For subjects randomized to favipiravir collect blood sample for PK analysis at 30 minutes prior to any dose
- Collect and record adverse events (see Section 8.4 for detailed instructions)
- Collect and record SpO2 by Finger Sensor
- Assess and record clinical status according to the following study-specific 6-point scale:
 - 1. Not hospitalized
 - 2. Hospitalized, not requiring supplemental oxygen
 - 3. Hospitalized, requiring supplemental oxygen
 - 4. Hospitalized, on non-invasive ventilation or high flow oxygen devices
 - 5. Hospitalized, on invasive mechanical ventilation or ECMO
 - 6. Death
- Assess and record NEWS2
- Assess and record ECOG Performance Status and Study-specific Symptom Status (see Appendix A).
- Collect and record adverse events (see Section 8.4 for detailed instructions).

7.4 Days 3, 8 and 11

- Collect blood samples for hematology and clinical chemistry laboratory analyses
- On Day 8 ± 1 day only: For subjects randomized to receive favipiravir, collect blood samples for PK trough analysis at 30 minutes prior to any dose
- On Days 3 and 11 ± 1 day: For subjects randomized to receive favipiravir, collect blood samples for PK peak analysis at 45-75 minutes after any dose.
- Measure and record vital signs (BP, HR, Temp, Resp).
- Perform a limited PE to focus on heart and lungs.
- Review and record concomitant medications (Note: if there have been changes in concomitant medications during the study, determine whether the change is due to an AE).
- Collect and record SpO2 by Finger Sensor
- Assess and record clinical status according to the study-specific 6-point scale:
 - 1. Not hospitalized
 - 2. Hospitalized, not requiring supplemental oxygen
 - 3. Hospitalized, requiring supplemental oxygen
 - 4. Hospitalized, on non-invasive ventilation or high flow oxygen devices
 - 5. Hospitalized, on invasive mechanical ventilation or ECMO
 - 6. Death
- Assess and record NEWS2
- Collect nasopharyngeal and oropharyngeal swabs for virologic testing.
- Collect and record adverse events (see Section 8.4 for detailed instructions).
- Assess and record ECOG Performance Status and Study-specific Symptom Status (see Appendix A).

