- 11. Days 3, 8, 11 Nasopharyngeal and Oropharyngeal Swabs for Viral RNA, PCR and TCID₅₀ may be done +/- 1 day from their scheduled day. Swabs will also be obtained on day of discharge from hospital if discharge occurs before Day 15.
- 12. To be checked throughout hospitalization and at clinic visits and changes only recorded as applicable.

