## 3.11. Visit Windows

It is expected that all visits should occur according to the protocol schedule. However, analysis visits will be derived based on study day for all by-visit summaries and analyses. Analysis visit designations are detailed in [Table 3-1](#).

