**Table 3-1 Post-Baseline Analysis Visit Designations**

| Analysis Visit | Analysis Visit Range |
|-----------------------|-----------------------------|
| Day 1                 | Day 1                       |
| Day 2                 | Day 2                       |
| Day 3                 | Days 3-5                    |
| Day 8                 | Days 6-9                    |
| Day 11                | Days 10-12                  |
| Day 15                | Days 13-17                  |
| Day 21                | Days 18-24                  |
| Day 29                | Days 25-33                  |
| Day 45                | Days 34-52                  |
| Day 60                | Days 53-70                  |

In the event there are multiple assessments within a given analysis range, the value closest to the target day (understood to be the day identified in the analysis visit) will be chosen. If more than one measurement are the same distance from the target day, the earlier visit will be chosen.

In data listings, the relative day of all dates will be presented.

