### **4.3. Efficacy Evaluation**

#### **4.3.1. Analysis of the Primary Efficacy Endpoint**

The primary endpoint of time to viral clearance will be analyzed with the log-rank test for treatment difference based on a two-sided alpha-level of 0.10 and summarized using Kaplan-Meier methodology. The time to viral clearance (in days) is defined as the time of Negative or Lower Limit of Quantification (LLOQ) results (without any quantitative results after that) as measured by PCR for SARS-CoV-2 via scheduled nasopharyngeal and oropharyngeal swab samples minus the date of first dose + 1.

Subjects who have no evidence of viral clearance will be censored at the time of the last PCR measurement with the following conditions:

- Patients whose symptoms worsen (defined as an increase of  $\geq 1$  point on the 6-point Ordinal Scale from baseline) on the day of the last PCR measurement, or who die will be censored at Day 29,
- Patients who are lost to follow-up will be censored on the day of the last PCR measurement.

The median time to viral clearance will be estimated based on the Kaplan-Meier estimator; additional summary statistics will be presented, including the 25th and 75th percentiles, 90% CIs (the log-log transformation) on the median and other percentiles and proportion of censored subjects. Viral clearance rates at Days 3, 8, 11, 15, and 29 will also be presented.

The analysis of the primary efficacy endpoint will be done using the ITT population.

The primary analysis will be supplemented with a sensitivity analysis, using a stratified log-rank test, where the treatment difference based on a two-sided alpha-level of 0.10 will be summarized and stratified by disease severity.

The analysis will also be repeated by the dexamethasone usage subgroup, where patients will be categorized as having received dexamethasone if they received it at any time prior to the last viral clearance assessment.

Kaplan-Meier curves will be provided for the overall ITT population. By-subject data listings of viral clearance data will also be provided.

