#### 4.3.2.9. Change in SARS-CoV-2 Viral Load

The change in SARS-CoV-2 viral load in upper respiratory tract specimen as assessed by area under viral load curve (quantitative PCR) as assessed up to 29 days. The area under the curve (AUC) over time for a given subject will be calculated, using the linear trapezoidal rule, as the sum of the maximum viral load for each day up through Day 29. Lower Limit of Quantification (LLOQ) result is considered as negative. An analysis of treatment group differences will be performed on the change in viral load using ANOVA model, with treatment group and disease severity as fixed factors.

The change in SARS-CoV-2 viral load will be analyzed by comparing the change between treatment groups using a mixed model with repeated measures (MMRM). This analysis will assess whether or not there is a difference in estimated change from baseline values between active treatment and SOC by visit using least squares means estimates from the MMRM. SAS PROC MIXED will be used to fit an MMRM with change from baseline in SARS-CoV-2 viral load as the response variable and the following covariates and fixed effects:

- Baseline SARS-CoV-2 viral load (covariate)
- Treatment group (fixed effect)
- Visit (fixed effect, time will be defined in terms of Visits)
- Time by Treatment Interaction (Time\*Treatment)

The covariance structure for the repeated measures in this model will be unstructured (UN). If UN does not converge for the model, a first-order autoregressive (AR(1)) covariance structure will be used.

Changes in viral load will be analyzed using the mITT population.

By-subject data listings will also be provided.

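### A Day 3 swab taken on Day 2 is within protocol, but SAP Table 3-1 analyses it as Day 2, a visit with no scheduled swab

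*Protocol*

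**What the plan says.** **Collection.** Note 11 to the schedule (Protocol Section 13) says that the Day 3, 8 and 11 swabs "may be done +/- 1 day from their scheduled day". The SAP reproduces the note under its own Table 1-1. Neither schedule has a swab on Day 2. Protocol Section 7.7 adds a swab on the day of discharge, whichever study day that is. For PK peaks, Protocol Section 7.4 reads "On Days 3 and 11 ± 1 day: For subjects randomized to receive favipiravir, collect blood samples for PK peak analysis".

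**Assignment to visits.** SAP Section 3.11 states that "analysis visits will be derived based on study day for all by-visit summaries and analyses". In Table 3-1, Day 2 is a one-day window and Day 3 covers Days 3-5. If a window holds several values, "the value closest to the target day (understood to be the day identified in the analysis visit) will be chosen", and "If more than one measurement are the same distance from the target day, the earlier visit will be chosen".

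**Use.** The viral-load model in SAP Section 4.3.2.9 includes "Visit (fixed effect, time will be defined in terms of Visits", a visit-by-treatment interaction and an unstructured covariance, with AR(1) if that does not converge. SAP Section 4.3.1 adds that "Viral clearance rates at Days 3, 8, 11, 15, and 29 will also be presented".

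**The concern.** The collection rule and the analysis rule disagree at one edge. A site that swabs on Day 2 has followed the schedule, but the SAP files the result under a visit for which no swab and no clearance rate are planned. The subject then has no observed value at Day 3, the earliest scheduled post-baseline look at viral load.

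The second effect is on the model. A few Day 2 values create an extra level of the visit factor. Almost nobody would have both a Day 2 and a Day 3 value, so the covariance between those two levels would have little or no data behind it. If the Day 2 values all came from one arm, the Day 2 treatment contrast could not be estimated. A labelling rule, not the biology, could then push the model to its fallback covariance.

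**Working it through.** **Step 1: compare the windows.** The collection windows come from the Protocol Section 13 schedule and note 11, and the analysis windows from SAP Table 3-1. The visits with scheduled post-baseline swabs are:

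| Visit | Collection tolerance | Permitted days | SAP window | Contained? |
|---|---|---|---|---|
| Day 3 | ±1 | 2-4 | 3-5 | No: Day 2 falls outside |
| Day 8 | ±1 | 7-9 | 6-9 | Yes |
| Day 11 | ±1 | 10-12 | 10-12 | Yes |
| Day 15 | -1 to +2 | 14-17 | 13-17 | Yes |
| Day 29 | ±2 | 27-31 | 25-33 | Yes |

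Days 45 and 60 have no swab, but their windows also fit: 43-47 within 34-52, and 58-62 within 53-70. Day 3 is the only visit with a permitted window that spills into another analysis visit.

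**Step 2: follow one compliant early swab.** It is taken on Day 2 and labelled Day 2. With no other swab on Days 3-5, the subject has no Day 3 value. If the subject is discharged on Day 3, 4 or 5, the discharge swab becomes the Day 3 value.

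**Step 3: effect on the model.** With v post-baseline visits, an unstructured matrix has v(v+1)/2 parameters.

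- As scheduled, v = 5 (Days 3, 8, 11, 15, 29): 5 × 6 / 2 = 15.
- With a Day 2 level, v = 6: 6 × 7 / 2 = 21.
- The 6 new parameters are one variance and five covariances. The Day 2/Day 3 covariance is informed only by subjects with a swab on Day 2 and another on Days 3-5.
- Visit-by-arm means rise from 5 × 2 = 10 to 6 × 2 = 12.

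**Step 4: how easily a Day 2 level arises.** The documents give no rate of early swabs. As an assumption, let each of 50 subjects independently have probability q of an early swab. The chance of at least one is 1 - (1 - q)^50:

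| q (assumed) | Expected early swabs, 50q | Chance of at least one |
|---|---|---|
| 2% | 1 | 0.636 |
| 5% | 2.5 | 0.923 |
| 10% | 5 | 0.995 |

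These are chances that the extra level appears, not that the model fails. The model uses the mITT population, which may be smaller than 50, and the chances would then be lower.

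**Step 5: after the change.** With a Day 3 window of Days 2-5 and no Day 2 visit for swabs, Days 2, 3 and 4 all map to Day 3 and the matrix stays at 15 parameters.

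**The case against.** The case for leaving the table alone has substance. A swab taken on Day 2 and labelled Day 2 carries its true study day, and deriving visits from study day is a stated choice. The value is not lost. It stays in the mixed model as Day 2, in the listings, in the AUC (which SAP Section 4.3.2.9 builds day by day) and in the primary analysis (which SAP Section 4.3.1 runs on dates). The Day 3 clearance rate can be read from the Kaplan-Meier curve, where an early swab does no harm. The fallback covariance is pre-specified, and SAP Section 3.2 makes every p-value except the primary one descriptive. A wider window also has a price: a Day 2 scheduled swab and a Day 4 discharge swab now fill two visits but would compete for one.

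All of that stands, and it limits the point to by-visit virology. It does not remove the mismatch: the SAP repeats the swab tolerance in Table 1-1 and then uses a table that does not accommodate it.

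A reader might also infer that PK peaks are discarded, because a Day 3 peak drawn on Day 2 would share a visit with the Day 2 trough (Protocol Section 7.3: "For subjects randomized to favipiravir collect blood sample for PK analysis at 30 minutes prior to any dose") and the tie rule keeps one value. The documents do not support that.

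- The tolerance in Section 7.4 may attach to Day 11 alone. Protocol Section 8.3 and schedule note 6 give none for the peaks.
- Both samples may be taken around any dose, so the earlier one could be the peak.
- A one-value rule cannot sensibly govern PK. Day 1 already has a pre-dose and a post-dose sample, and SAP Section 4.4 reports a Day 14 that Table 3-1 lacks.

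**Conclusion.** The mismatch for swabs is real and minor. Following the plan as written moves compliant early Day 3 swabs into an unscheduled Day 2 visit. It leaves those subjects without a Day 3 viral load unless a discharge swab intervenes. It can also load the unstructured model with a level it cannot support, which makes the AR(1) fallback more likely but not certain.

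The reach is the secondary viral-load model, and the Day 3 clearance rate if that is computed by visit. It would be tempting to say that valid Day 3 data are dropped or that the primary result is at risk. Neither follows, since the values remain in every date-based or day-based analysis. The size in practice depends on the number of early swabs, which the documents do not give. No change in a conclusion has been shown.

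**What to change.** In SAP Table 3-1, add a rule for swab-based assessments only (PCR, viral load, TCID50): the Day 3 window is Days 2-5, and there is no Day 2 visit. Keep the separate Day 2 visit for the daily assessments, such as the 6-point scale, NEWS2 and vital signs.

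State also that when a scheduled Day 3 swab and a discharge swab both fall in this window, the scheduled swab is the Day 3 value. The existing rules already give that result for a Day 2 scheduled swab against a discharge swab on Day 4 (tie, earlier kept) or Day 5 (distance 2 against 1). They would not for a discharge on Day 3 (distance 0 against 1), so the preference must be written down.

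At most, add one sentence that PK is summarised by nominal sample.

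The cost is a few lines of SAP text and one programming rule, with no new data. The downside is small: a discharge swab on Days 3-5 may not enter the by-visit model when an early scheduled swab exists, though it stays in the date-based analyses. The rule should be fixed before viral loads are examined, because the trial is open label.

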7.5 Days 15 and 29 (Follow-up) or Early Termination

- Perform a limited PE to focus on heart and lungs.
- Review and record concomitant medications (Note: if there have been changes in concomitant medications during the study, determine whether the change is due to an AE).
- Measure and record vital signs (BP, HR, Temp, Resp).
- Collect and record SpO2 by Finger Sensor
- Collect blood samples for:
 - o Antibodies to SARS-CoV-2.
 - o Hematology and clinical chemistry laboratory analyses
- Assess and record clinical status according to the following study-specific 6-point scale:
 - 1. Not hospitalized
 - 2. Hospitalized, not requiring supplemental oxygen
 - 3. Hospitalized, requiring supplemental oxygen
 - 4. Hospitalized, on non-invasive ventilation or high flow oxygen devices
 - 5. Hospitalized, on invasive mechanical ventilation or ECMO
 - 6. Death
- Assess and record NEWS2
- Collect nasopharyngeal and oropharyngeal swabs for virologic testing.
- Collect and record adverse events (see Section 8.4 for detailed instructions).
- Assess and record ECOG Performance Status and Study-specific Symptom Status (see Appendix A).

Note: Day 15 visit procedures may be conducted on Day 14 if patient is discharged before Day 15.

7.6 Days 45 and 60 (Additional Safety Follow-up)

Follow up assessment of general health and well-being may be done while the subject remains hospitalized or by phone if the subject has been released from the hospital and is unable to return for the study visit.

- Measure and record vital signs (BP, HR, Temp, Resp).
- Perform a limited PE to focus on heart and lungs.
- Review and record concomitant medications (Note: if there have been changes in concomitant medications during the study, determine whether the change is due to an AE).
- Collect and record SpO2 by Finger Sensor
- Assess and record clinical status according to the following study-specific 6-point scale:
 - 1. Not hospitalized
 - 2. Hospitalized, not requiring supplemental oxygen
 - 3. Hospitalized, requiring supplemental oxygen
 - 4. Hospitalized, on non-invasive ventilation or high flow oxygen devices
 - 5. Hospitalized, on invasive mechanical ventilation or ECMO
 - 6. Death
- Assess and record NEWS2
- Administer the ECOG Performance Status questionnaire. (See Appendix A)
- Administer the Study-specific Symptom Status questionnaire. (See Appendix A)

• Collect and record adverse events (see Section 8.4 for detailed instructions).

NOTE: if the visit is conducted by phone, vital signs, limited PE, SpO2, and NEWS2 will not be evaluated.

7.7 Day of Discharge from Hospital

- Some subjects may be well enough for discharge from the hospital prior to completing the full 14 days of treatment. In these cases, the following procedure should be followed
- FOR ALL SUBJECTS (regardless of treatment assignment)
 - O The study staff will collect nasopharyngeal and oropharyngeal swabs, regardless of which study day the subject is discharged (e.g., samples should be collected on subjects discharged from the hospital on Study Day 4 even though they will have had this procedure on Study Day 3, per protocol.)

FOR SUBJECTS TAKING FAVIPIRAVIR

- O The study staff will request the pharmacy to dispense the appropriate number of tablets for the subject to take between the time of discharge and the next scheduled study visit plus one extra day in case the visit must be changed. Prior to each study visit, the study staff will request a "refill" of favipiravir tablets to be taken by the subject between the time of the current visit and the subsequent visit. (See Pharmacy Instructions for details of dispensing.)
- To assist the subject with compliance, dosing instructions will be provided along with the favipiravir.
- O Subjects will be reminded that the Rx bottle MAY NOT BE RETURNED TO (LEFT AT) THE SITE. To avoid contamination, each subject will bring the bottle and unused drug to their visit and show the contents of the bottle to the study staff conducting the visit. Once the drug has been counted, the subject will be instructed to dispose of the pills by placing them in a separate bag and putting the bag in the on-site trash.
- o NOTE: the site may make modifications to this procedure if needed to comply with local rules for non-contamination of the site.
- When a subject completes dosing (either by completing all 14 days of dosing or by leaving the study) the pharmacy will send the Subject IP accountability log to the Sponsor for verification with the EDC and compliance with the protocol.

8 EFFICACY, PHARMACOKINETICS AND SAFETY ASSESSMENTS

8.1 Efficacy Assessments

Efficacy will be assessed by the following measurements:

- Presence of virus in the nasopharyngeal and oropharyngeal samples taken on Days 1, 3, 8, 11, 15 and 29 (if hospitalized and when able to return to clinic after discharge). Swabs will also be obtained on day of discharge from hospital if discharge occurs before Day 15.
- Clinical improvement of hospitalized subjects with COVID-19 receiving either favipiravir + SOC or SOC alone as defined by the following study-specific 6-point ordinal scale at Day 15

- 1. Not hospitalized
- 2. Hospitalized, not requiring supplemental oxygen
- 3. Hospitalized, requiring supplemental oxygen
- 4. Hospitalized, on non-invasive ventilation or high flow oxygen devices
- 5. Hospitalized, on invasive mechanical ventilation or ECMO
- 6. Death
- Status on the study specific 6-point ordinal scale assessed daily while hospitalized and at each outpatient visit until Day 60.
- NEWS2 assessed daily while hospitalized and at each outpatient visit until Day 60.
- Patient status assessed daily while hospitalized and at each outpatient visit until Day 60 via Study-specific Symptom Status and the ECOG Performance Status questionnaires (see Appendix A).
- Duration of supplemental oxygen (if applicable).
- Duration of mechanical ventilation (if applicable).
- Duration of hospitalization.
- Date and cause of death (if applicable).
- PCR and TCID50 in nasopharyngeal and oropharyngeal swabs on Days 1, 3, 8, 11, 15 and 29 (if hospitalized and when able to return to clinic after discharge), and on day of discharge if hospital discharge occurs before Day 15.
- Blood for determination of antibodies to SARS-CoV-2 obtained on Days 1, 15 and 29 (if hospitalized and when able to return to clinic after discharge).

8.2 Required Resistance Testing

Resistance testing, as required in clinical trials of anti-viral drugs will be performed using one of the swabs, at each time point that nasopharyngeal and oropharyngeal swabs are taken.

8.3 Pharmacokinetics/Pharmacodynamics Assessments

- 6.0 mL of blood will be collected for PK sampling on:
 - o Day 1 pre- and post-dosing (1st dose)
 - O Days 2, 8 and 14 pre-dosing (any dose)
 - o Days 3 and 11 post-dosing (any dose)
- Kits for each PK draw and instructions for handling and shipping are provided by the PK analysis laboratory.

8.4 Safety Assessments

Abnormal clinical laboratory values that are clinically significant and all reported adverse events will be graded according to the Common Terminology Criteria for Adverse Events (CTCAE) version 5.0.

Safety will be assessed by the collection of observed and reported adverse events, physical exams, vital signs, and the following clinical laboratory tests:

Hematology

Hemoglobin (Hgb) Hematocrit (Hct)
Platelet count Red blood cell count

White blood cell count with differential

Chemistry

Blood Urea Nitrogen (BUN) Creatinine

Total bilirubin Alkaline Phosphatase

Aspartate transaminase (AST)

Gamma-glutamyl transferase (GGT)

Alanine transaminase (ALT)

Lactic dehydrogenase (LDH)

Glucose Albumin
Total protein Bicarbonate
Phosphate Sodium
Potassium Chloride

Calcium Total cholesterol
Urate C-reactive protein

D-dimer

NOTES:

• All clinical laboratory assessments listed above (hematology and chemistry) will be conducted at each site's local clinical laboratory.

• If coagulation assays are ordered as part of the SOC, the results should be added to the EDC.

Including PK and Clinical Laboratory Testing, subjects will undergo 9 planned venipunctures during this study.

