2.3 Clinical Experience

Overall, more than 40 clinical studies with favipiravir have been conducted globally, mainly in the US and Japan. Recently, China has begun studying favipiravir in patients with severe influenza as well as COVID-19. More than 3100 study subjects have received at least one dose of favipiravir manufactured by Toyama Chemical. Favipiravir has been well tolerated in studies

in adults and elderly subjects with uncomplicated influenza. A consistent safety profile composed of relatively low frequencies of mild to moderate adverse events (AEs) clustering around the system organ classes of gastrointestinal disorders, investigations, and infections and infestations has been characterized. Mild to moderate transient, asymptomatic elevations in serum uric acid and mild to moderate diarrhea are the two most common AEs known to occur with favipiravir. In double blind studies, the adverse event profile of favipiravir and placebo were similar with the exception of elevations of uric acid. Details can be found in the Investigator's Brochure.

Favipiravir has been used in an open label study in patients with Ebola, (2400 mg twice eight hours apart, followed by 1200 mg 8 hours later and then 1200 mg BID for the following 9-13 days). Although conclusions about efficacy cannot be reached because of the lack of a concurrent control group, favipiravir at this regimen appeared to be well tolerated. A study in Japan in patients with Severe Fever with Thrombocytopenia administered 1800 mg BID Day 1 followed by 800 mg BID for the next 13 days. It has also been used under compassionate use in patients with rabies or other unusual RNA virus illnesses.

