3 DESIGN

This is an open label, randomized, controlled, multicenter Phase 2 study of favipiravir in hospitalized subjects with COVID-19. Subjects will be randomized within their study site and stratified by the severity of their disease to receive either favipiravir + standard of care (SOC) or SOC alone (See Section 9.5 for details).

SOC will be site-specific and based on what each site is currently using for COVID-19 patients.

The dose regimen will be 1800 mg favipiravir BID plus SOC or SOC alone on Day 1 followed by 1000 mg BID favipiravir (800 mg BID for subjects with Child-Pugh A liver impairment) plus SOC or SOC for the next 13 days.

The study will have 14 days of treatment and 46 days of follow-up.

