8.6 Clinical Laboratory Abnormalities and Other Abnormal Assessments

Laboratory abnormalities are usually not recorded as AEs unless considered to be clinically significant by the site clinician. An abnormal laboratory result will be considered an AE if it induces clinical signs or symptoms, if the abnormality is of a degree that requires active management (e.g. discontinuation of the study drug, dose modification) or when the event is requiring treatment or other therapeutic intervention (e.g. iron supplements, blood transfusion, etc.).

The Investigator will evaluate the relationship of any significantly abnormal result to protocol treatment and clinical condition, if possible. All clinically significant abnormal laboratory results will be followed until they return to normal or become stabilized.

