9.7 Safety Analysis

The original exact terms in the electronic data capture (EDC) system used by Investigators to identify AEs other than symptoms of COVID-19 will be fully described and coded according to the Medical Dictionary for Regulatory Activities (MedDRA). Treatment-emergent AEs will be defined as those occurring coincident with start of treatment and through Day 60. TEAEs will be summarized overall and by treatment group and by MedDRA body organ system and preferred term, severity, relatedness, and seriousness.

An overall summary of TEAEs will be presented by treatment, with subject counts and percentages of subjects with the event. This summary will include subjects with any TEAE, any treatment-related TEAE, any serious TEAE, any treatment-related serious TEAE, TEAEs leading to study infusion discontinuation, treatment-related TEAEs leading to study infusion discontinuation, TEAEs leading to death, and treatment-related TEAEs leading to death. The difference in proportions between treatment groups in each of these categories will be calculated.

Summaries of changes over time in laboratory parameters, as well as counts and percentages of laboratory parameters that are Low, Normal, and High compared to the reference ranges will be presented by treatment at each visit and time point. Shift tables will be presented for laboratory parameters with defined severity grades.

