#### 4.5.3. Laboratory Data

Clinical laboratory values will be expressed in SI units.

All laboratory data will be provided in data listings.

Abnormal clinical laboratory values that are clinically significant will be graded according to the CTCAE version 5.0. A listing of all abnormal laboratory values will be provided.

Shift tables for hematology and chemistry parameters from baseline to worst value will be provided by treatment group and overall. All unscheduled visits, if any, will contribute to the last or worst value.

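### CTCAE grading covers only laboratory values deemed clinically significant, by no stated criterion and in an open-label trial, and the SAP leaves its laboratory shift categories undefined

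*Protocol*

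**What the plan says.** **Which values are graded.** Protocol 8.4: "Abnormal clinical laboratory values that are clinically significant and all reported adverse events will be graded" according to CTCAE version 5.0. SAP 1.2.6.3 has the same rule, and SAP 4.5.3 repeats it for laboratory data: "Abnormal clinical laboratory values that are clinically significant will be graded according to the CTCAE version 5.0". None of the three places says what makes a value clinically significant or who decides.

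**Who decides, where anyone is named.** Protocol 8.6: "Laboratory abnormalities are usually not recorded as AEs unless considered to be clinically significant by the site clinician". That sentence is about recording a laboratory abnormality as an adverse event. The section adds further triggers: signs or symptoms, a need for active management, or a need for treatment. Protocol section 3 gives the blinding: "This is an open label, randomized, controlled, multicenter Phase 2 study of favipiravir in hospitalized subjects with COVID-19".

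**What is tabulated.** Protocol 9.7: "Shift tables will be presented for laboratory parameters with defined severity grades". The same paragraph plans summaries of change over time and, by treatment and visit, counts of values that are low, normal or high against the reference range. SAP 4.5.3: "Shift tables for hematology and chemistry parameters from baseline to worst value will be provided by treatment group and overall". It also plans a listing of all laboratory data and a listing of all abnormal values.

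**What is expected.** Protocol 2.3 names "Mild to moderate transient, asymptomatic elevations in serum uric acid" as one of the two most common adverse events known for favipiravir. It adds that uric acid was the exception to otherwise similar favipiravir and placebo profiles in double-blind studies.

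**The concern.** A CTCAE grade is useful in a two-arm safety comparison because it applies one scale to every subject. Here a value must first be called clinically significant before it is graded. No criterion is given, and the staff likely to make that call know the assignment. Two things can then go wrong in a table built on the grades. An asymptomatic change, which is how the protocol describes the drug's best-documented laboratory effect, may never receive a grade. And the two arms may be graded with different vigilance, so that a difference between them partly reflects who was watched more closely.

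Safety against SOC is a stated secondary objective (Protocol 4.2), and the SAP is the stated basis for the results in the study report (SAP 1.1.2). It therefore matters whether the laboratory table that the SAP does specify rests on all values or on flagged ones.

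**Working it through.** The plan attaches no figure to this point, so the check is a comparison of passages.

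1. **The restriction is explicit and consistent.** Protocol 8.4, SAP 1.2.6.3 and SAP 4.5.3 all limit grading to abnormal values that are clinically significant. This is a positive rule, not a gap.

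2. **The decision-maker is inferred.** Only Protocol 8.6 names one, the site clinician, and it does so for adverse event recording. Carrying this over to grading is reasonable because no other assessor appears, but it is not written.

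3. **The shift tables need something the rule does not supply.** A baseline-to-worst table needs a category for each subject at baseline and at the worst value. Selective grading gives a category only to flagged values. Protocol 9.7 selects tables by parameter and does not exclude unflagged values. SAP 4.5.3 does not say whether its categories are CTCAE grades or Low/Normal/High. As written, a programmer cannot tell how to classify an unflagged abnormal value.

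4. **Protocol and SAP laboratory outputs side by side.**

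| Output | Protocol 9.7 | SAP 4.5.3 |
|---|---|---|
| Change over time | planned | not mentioned |
| Low/Normal/High counts by arm and visit | planned | not mentioned |
| Shift table | parameters with severity grades | baseline to worst, categories undefined |
| Listing of all abnormal values | not mentioned | planned |

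SAP 4.5.4 does specify values and changes from baseline for vital signs, so their absence for laboratory data is noticeable. SAP 3.3 promises tabulations of appropriate safety parameters only in general terms. SAP Section 5 declares one change from the protocol, the removal of hierarchical testing. The shift table is thus the only laboratory summary table that SAP 4.5.3 names, and its categories are undefined.

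5. **What could happen, in symbols.** Suppose the table uses grades and reads an ungraded value as no shift. This is an assumption; no passage says so. Let p be the true share of subjects in an arm whose value crosses a grade limit, and f the share of those that the site flags. The table then shows p × f. The displayed difference is p(fav) × f(fav) − p(SOC) × f(SOC). With equal true rates p in both arms it becomes p × [f(fav) − f(SOC)], which is not zero unless flagging is equal. The documents give neither p nor f, so no number follows.

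6. **Sensitivity to single subjects.** Protocol 9.2 plans 25 subjects per arm. One subject classified differently moves that arm's percentage by 1/25 = 4 points.

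**The case against.** A reader might infer that the shift tables leave out unflagged values, and so hide the uric acid signal. The documents do not support that. Protocol 9.7 chooses parameters, not flagged values, and SAP 4.5.3 speaks of the worst value and lets unscheduled visits contribute. The text is ambiguous; it does not exclude anything. This part of the objection stands.

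It also stands that the values are captured without a site filter elsewhere. The protocol's High column would count each uric acid result above the reference range, and the SAP lists every abnormal value. The reply is limited but real: listings do not compare the arms, and SAP 4.5.3 does not carry over the two protocol summaries that would.

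A reader might also extend the point to liver enzymes. The documents set AST and ALT stopping limits (Protocol 5.4) but do not describe such rises as expected; only uric acid rises are described that way.

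It can further be said that sites may well flag uric acid. Protocol 2.3 reports it as a common adverse event in past studies, and all reported adverse events are graded. That is fair, and flagging behaviour cannot be predicted from the documents. The further triggers in Protocol 8.6 also bring some values in, including those that reach the numeric stopping limits. They do not cover asymptomatic, untreated rises below those limits. Moreover, stopping or modifying study drug, the examples given for active management, can occur only in the favipiravir arm.

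Finally, the trial is an exploratory proof of concept with about 50 subjects, and no test or decision rule depends on laboratory grades. That limits the importance of the point but does not remove it.

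**Conclusion.** The point holds in a limited form. Grading of laboratory values depends on an undefined judgement in an open-label trial, and the SAP does not say whether its shift tables use those grades. A table built on them may miss asymptomatic changes and may differ by arm through site opinion. Separately, the SAP silently omits two protocol summaries that would compare the arms without any site filter.

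The conclusion rests on two readings: that clinical significance is decided at the site for grading as it is for adverse events, and that the shift tables might be built on CTCAE grades. Neither is written outright. No size can be given beyond the 4 points per subject in an arm of 25. This is not evidence that data are lost or that a safety signal will be concealed. It is a modest weakness in a descriptive analysis, worth correcting because the correction is cheap.

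**What to change.** - In Protocol 8.4, SAP 1.2.6.3 and SAP 4.5.3, delete the qualifier on clinical significance from the laboratory grading sentence.
- State that grades are derived by program, in both arms, from every value (baseline included) and the local reference range, for each parameter that can be graded from the number.
- In SAP 4.5.3, define the shift categories: CTCAE grade where it can be derived from the number, and Low/Normal/High where it cannot. The documents do not reproduce the CTCAE tables, so which group urate falls into must be checked against version 5.0.
- Restore in SAP 4.5.3 the protocol's Low/Normal/High counts and change-over-time summaries by arm and visit.
- Keep site judgement only for deciding whether a laboratory value is also an adverse event.

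Cost: wording changes in both documents, some programming, and more low-grade entries in the tables. No new measurements are needed, assuming that the local reference ranges are collected. The protocol's own Low/Normal/High counts already require them.
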